9.5 Prior and Concomitant Medications

Information regarding prior and concomitant medications, including CF medications, other medications, and herbal and naturopathic remedies, will be collected from each subject's source documentation for medications taken within 56 days before the Screening Visit through completion of study participation, as defined in Section 9.1.7. Medications will be categorized as defined in Section 12.3.2.3.

For subjects who are screened but are not subsequently randomized, details of prior medication will be documented only in the subjects' source documents.

- Subjects should remain on a stable treatment regimen for their CF from 28 days before the Day -28 Visit through completion of study participation. Stable treatment regimen is defined as the current treatment regimen for CF that subjects have been following for at least 28 days before the Day -28 Visit. Subjects who are on Vertex CFTR modulators (investigational or approved) at the date of informed consent may remain on these during the Screening Period and should transition directly to study drug at the beginning of the Run-in Period on Day -28 without a washout (Table 9-3). Subjects should not initiate long-term treatment with new medication from 28 days before the Day -28 Visit through completion of study participation. Guidelines for stable treatment regimens for CF are as follows:

- o Subjects who are taking inhaled tobramycin or other chronically inhaled antibiotics should remain on that regimen throughout the study.
- o Subjects who cycle onto and off of an inhaled antibiotic should continue on their prior schedule. The timing of the first dose of study drug on the Day 1 Visit should be synchronized as closely as possible (e.g., not more than ± 3 days) to the first day in the cycle onto the inhaled antibiotic.
- o Subjects who alternate between 2 different inhaled antibiotics should remain on the same cycling schedule during the study. The timing of the first dose of study drug on the Day 1 Visit should be synchronized as closely as possible (e.g., not more than ± 3 days) to the first day in the cycle onto 1 of the inhaled antibiotics.
- Subjects may receive doses of prednisone or prednisolone of up to 10 mg/day chronically, or up to 60 mg daily for up to 5 days.
- VX-445 may inhibit OATP1B1 and OATP1B3, which may increase the exposure of medicinal products that are substrates for these transporters. Substrates such as statins, glyburide, nateglinide, and repaglinide should be used with caution.
- IVA is a weak inhibitor of P-glycoprotein (P-gp). Administration of IVA may increase systemic exposure of medicinal products that are sensitive substrates of P-gp, which may increase or prolong their therapeutic effect and adverse reactions. Digoxin or other substrates of P-gp with a narrow therapeutic index, such as cyclosporine, everolimus, sirolimus, and tacrolimus, should be used with caution and appropriate monitoring.
- IVA may inhibit CYP2C9; therefore, during coadministration with warfarin, additional monitoring of the international normalized ratio is recommended. Other medicinal products that are CYP2C9 substrates for which exposure may be increased include glimepiride and glipizide; these should be used with caution.
- Information about bronchodilator use during the study will be collected and documented. Subjects who are using a bronchodilator must have their spirometry assessments performed according to the guidelines provided in Section 11.5.1.

9.6 Administration

9.6.1 Dosing

Study drug will be administered orally. All subjects will receive the same number of tablets each day during the Treatment Period to maintain the blind. Additional information is provided in the Pharmacy Manual.

Study drug should be administered with a fat-containing meal or snack, such as a standard “CF” meal or snack or a standard meal.

1. It is recommended that the dose be taken within 30 minutes of the start of the meal or snack.
2. In the IVA comparator group, study drug in the Run-in Period will be administered as 1 IVA tablet in the morning and 1 IVA tablet in the evening. Study drug in the Treatment Period will be administered as 2 fixed-dose combination (FDC) TC tablets or matching placebo tablets and 1 IVA tablet or matching placebo tablet in the morning, and 1 IVA tablet in the

evening (Table 9-2). For each subject, doses of study drugs should be taken at approximately the same time (± 2 hours) each day.

3. In the TEZ/IVA comparator group, study drug in the Run-in Period will be administered as 1 TEZ/IVA FDC tablet in the morning and 1 IVA tablet in the evening. Study drug in the Treatment Period will be administered as 2 FDC TC tablets or matching placebo tablets and 1 TEZ/IVA FDC tablet or matching placebo tablet in the morning, and 1 IVA tablet in the evening (Table 9-2). For each subject, doses of study drugs should be taken at approximately the same time (± 2 hours) each day.
4. The date, amount taken, and time of study drug administration, including whether food was taken with each dose, will be recorded for the 2 doses before PK sample collection and the dose received on the morning of PK sample collection (if applicable).
5. On days of scheduled visits, the morning dose of study drug will be administered at the site after predose assessments have been completed. A meal or snack will be provided by the site for the morning dose of study drug.
6. If a subject's scheduled visit is to occur in the afternoon, the following guidelines should be used:
 - If the dose in the clinic will be within 6 hours of the subject's scheduled morning dose, the subject should withhold their morning dose of study drug and the morning dose will be administered in the clinic.
 - If the dose in the clinic will be more than 6 hours after the subject's scheduled morning dose, the subject should take the morning dose of study drug at home.
7. Subjects will be instructed to bring all used and unused materials associated with the study drug to the site; study drug will be dispensed at each visit, as appropriate.

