3 SCHEDULE OF ASSESSMENTS

Schedules of assessments are in [Table 3-1](#) and [Table 3-2](#).

All visits will be scheduled relative to the Day 1 Visit (first dose of randomized study drug in the Treatment Period). For example, the Week 8 (\pm 5 days) Visit would occur after 8 weeks of study drug administration in the Treatment Period has been completed.

The Cystic Fibrosis Questionnaire-Revised (CFQ-R) must be completed before any other assessment (except signing of the informed consent form [ICF]) at relevant clinic visits. Remaining assessments may be performed in any order when more than 1 assessment is required at a particular time point. All assessments will be performed before study drug dosing (Section 9.6.1), unless noted otherwise.

Table 3-1 Study VX18-445-104: Screening

Event/Assessment	Screening Period Day -56 Through Day -29	Comments
ICF and assent (when applicable)	X	
Inclusion and exclusion criteria review	X	Sections 8.1 and 8.2
Demographics	X	Section 11.1
Medical history	X	
CFTR genotype	X	Performed for all subjects (Section 11.6.2). In subjects with an R117H mutation, linkage to poly-T tract polymorphisms will also be determined from a second specimen. A subject's screening CFTR genotype must confirm eligibility before the subject enters the Run-in Period (Section 8.1).
FSH	X	Performed for any suspected postmenopausal female with at least 12 months of continuous spontaneous amenorrhea (Section 11.6.2)
Serum pregnancy test (all females)	X	Section 11.6.2
Hematology	X	
Coagulation	X	
Serum chemistry	X	
Urinalysis	X	
Weight and height	X	Measured with shoes off (Section 11.1)
OE	X	Conducted only for subjects who are <18 years of age on the date of informed consent (Section 11.6.6)
Complete physical examination	X	Section 11.6.3
Vital signs	X	Performed after subject has been at rest for at least 5 minutes (Sections 11.6.3, 11.6.4, and 11.6.5)
Pulse oximetry	X	
Standard 12-lead ECG	X	
Spirometry	X	May be performed pre- or post-bronchodilator (Section 11.5.1)
Medications review	X	Section 9.5
Sweat chloride	X	Section 11.3
AEs and SAEs	Continuous from signing of the ICF through completion of study participation	Sections 9.1.7, 13.1.1.3, and 13.1.2.2

AE: adverse events; FSH: follicle-stimulating hormone; ICF: informed consent form; OE: ophthalmologic examination; SAE: serious adverse event

Table 3-2 VX18-445-104: Run-in Period, Treatment Period, and Safety Follow-up Visit

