Vital signs	X		X	X	X	X	X	X	After subject has been at rest for at least 5 minutes and before dosing, as applicable (Sections 11.6.3 and 11.6.4)
Pulse oximetry	X		X	X	X	X	X	X	
Spirometry		X	X	X	X	X	X	X	Must be performed before dosing, and should be performed pre-bronchodilator (Section 11.5.1) at approximately the same time at each visit.
SwCl		X	X	X	X	X	X		Must occur before dosing. At each time point, 2 samples will be collected, 1 from each arm (left and right) (Section 11.3)
Urinalysis	X		X			X	X	X	Section 11.6.2
Hematology	X		X	X	X	X	X	X	Day -28 and Day 1: Blood samples will be collected before the first dose of study drug in each study period (Section 11.6.2)
Coagulation	X		X			X	X	X	
Serum chemistry	X		X	X	X	X	X	X	
PK sampling			X	X	X	X	X		Day 1, Day 15, and Week 4: Predose PK within 60 minutes before dosing (Section 11.2.1) Week 8: Predose PK within 60 minutes before dosing for subjects receiving their first dose of study drug in an open-label study. For other subjects, the blood sample should be collected approximately 12 hours after the evening dose of IVA before the Week 8 Visit (Section 11.2.1)
DNA sample (optional)			X						Section 11.4.1
Inflammatory mediator samples	X		X			X	X		Section 11.4.2

Table 3-2 VX18-445-104: Run-in Period, Treatment Period, and Safety Follow-up Visit

Event/Assessment ^a	Run-in Period (4 Weeks)		Treatment Period (8 Weeks)				ETT Visit ^b	Safety Follow-up Visit 28 (± 7) Days After the Last Dose of Study Drug (If Applicable) ^c	Comments
	Day -28 ± 1 Day	Day -14 ± 2 Days	Day 1 ^d	Day 15 ± 3 Days	Week 4 ± 5 Days	Week 8 ± 5 Days			
Blood biomarker samples	X		X			X	X		Section 11.4.3
Blood sample for RNA	X		X			X	X		
Sputum sample	X		X			X	X		Collected from subjects who can produce a sample spontaneously (Section 11.4.4)
Run-in dosing	Day -28 to evening on Day -1								A subject's screening CFTR genotype must confirm eligibility before the subject enters the Run-in Period (Section 9.1.2 and Section 11.6.2). Run-in dosing details for each comparator group are provided in Section 9.6.1.
Run-in drug count	X	X	X						Section 10.6
Randomization			X						Randomization may occur on either Day -1 or Day 1, after conditions for entry into the Treatment Period (Section 9.1.3) have been met.

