Randomized study drug dosing			Day 1 through evening before the Week 8 Visit						Subjects will be randomized 1:1 to the VX-445 200 mg qd/TEZ 100 mg qd/IVA 150 mg q12h arm or the control arm (IVA 150 mg q12h or TEZ 100 mg qd/IVA 150 mg q12h, depending on comparator group assignment) (Section 9.6.1).
Randomized study drug count			X	X	X	X	X		Section 10.6
Medications review	Continuous from signing of ICF through completion of study participation								Completion of study participation is defined in Section 9.1.7
Treatments and procedures review	Continuous from signing of ICF through completion of study participation								

Table 3-2 VX18-445-104: Run-in Period, Treatment Period, and Safety Follow-up Visit

Event/Assessment ^a	Run-in Period (4 Weeks)		Treatment Period (8 Weeks)				ETT Visit ^b	Safety Follow-up Visit 28 (± 7) Days After the Last Dose of Study Drug (If Applicable) ^c	Comments
	Day -28 ± 1 Day	Day -14 ± 2 Days	Day 1 ^d	Day 15 ± 3 Days	Week 4 ± 5 Days	Week 8 ± 5 Days			
AEs and SAEs	Continuous from signing of ICF through completion of study participation							Completion of study participation is defined in Section 9.1.7. Refer to Sections 13.1.1.3 and 13.1.2.2 for reporting and documentation of AEs and SAEs.	

Abbrev: abbreviated; AE: adverse event; CFQ-R: CF Questionnaire-Revised; ETT: Early Termination of Treatment; ICF: informed consent form; IVA: ivacaftor; OE: ophthalmologic examination; PK: pharmacokinetic; SAE: serious adverse event; SwCl: sweat chloride; TEZ: tezacaftor

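### The home-dosing guideline for late visits conflicts with the pre-dose rule for spirometry and SwCl at Day 15 and Week 4, and the SAP would use the resulting post-dose values unflagged

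*Protocol*

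**What the plan says.** **Dosing on visit days (Protocol 9.6.1).** Item 5 sets the default: "the morning dose of study drug will be administered at the site after predose assessments have been completed". Item 6 covers afternoon visits. If the clinic dose falls within 6 hours of the usual morning dose, the dose is withheld and given in clinic. If it would be later than that, "the subject should take the morning dose of study drug at home".

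**Measurement timing.** Section 3 gives the general rule: "All assessments will be performed before study drug dosing (Section 9.6.1), unless noted otherwise". The rows of Table 3-2 are more specific. For spirometry: "Must be performed before dosing, and should be performed pre-bronchodilator". For SwCl: "Must occur before dosing. At each time point, 2 samples will be collected". Both rows cover Day -14, Day 1, Day 15, Week 4 and Week 8. Section 11.3 repeats the pre-dose rule for every SwCl collection, and 11.5.1 repeats it for Treatment Period spirometry. Table 3-2 and 11.5.1 also ask for spirometry at about the same clock time at each visit.

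**Dosing spans (Table 3-2).** Run-in dosing: "Day -28 to evening on Day -1". Randomized dosing: "Day 1 through evening before the Week 8 Visit".

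**PK.** Section 11.2.1 sets a window of 60 minutes before dosing at Day 1, Day 15 and Week 4, asks sites to make every effort to meet it, and classes out-of-window samples as deviations. Under 9.6.1 item 4, dose times are recorded for the two doses before a PK sample and for any dose that morning.

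**Analysis.** The primary ppFEV₁ estimate averages Week 4 and Week 8 (SAP 9.3.1.2). The SwCl estimate averages Day 15, Week 4 and Week 8 (SAP 9.3.2.2). SAP Appendix A uses dose time for baseline only, including an allowance of up to 30 minutes after first dose for SwCl. Post-baseline values are chosen by distance from the target day.

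**The concern.** A subject who follows item 6 is measured more than 6 hours after the morning dose, at a visit whose spirometry and SwCl are required to be pre-dose. Item 6 mentions neither assessment and does not say whether to reschedule, skip or measure post-dose. Two sites could each follow the protocol and return values taken in different dosing states.

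The Day 1 baseline has no same-day dose before it. A home-dosed Week 4 ppFEV₁ value, or a home-dosed Day 15 or Week 4 SwCl value, therefore differs from baseline in dosing state as well as in treatment. The primary and first key secondary endpoints are within-group changes in the VX-445/TEZ/IVA arm, so no control arm subtracts such a shift. The between-group endpoints are less exposed, because item 6 applies to both arms.

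**Working it through.** **1. Which visits are affected**

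| Visit | Same-day morning dose possible before assessment? | Use of the value |
|---|---|---|
| Day -14 | Yes (within run-in dosing) | Stratification |
| Day 1 | No (run-in ends the evening before; first randomized dose follows the assessments) | Baseline |
| Day 15 | Yes | In both MMRMs; in the SwCl average only |
| Week 4 | Yes | In both averages |
| Week 8 | No (randomized dosing ends the evening before) | In both averages |

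Day -14 can only move a subject across the 70-point ppFEV₁ or 30 mmol/L SwCl stratum cut before randomization. The model uses continuous baseline values.

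**2. The plan's own power figure (Protocol 12.1)**

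Inputs: SD 7.0, difference 3.0, 125 subjects, 10% dropout, two-sided 0.05.

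- n = 125 × 0.9 = 112.5, taken as 112.
- Planning SE = 7.0/√112 = 0.661.
- One-sample t power (noncentral t) = 99.4%, which agrees with the stated >99%.

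**3. Weight of the affected visits**

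Let f be the share of late, home-dosed visits and s the post-dose minus pre-dose difference. The documents give neither. Assume f = 5-20%, which is 112 × 0.05 = 5.6 to 112 × 0.20 = 22.4 Week 4 values.

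- ppFEV₁: one affected visit of two, so the average moves by f × s/2. The fraction of s that reaches it is 0.025 (f = 5%), 0.05 (10%) or 0.10 (20%).
- SwCl: two affected visits of three, so the average moves by f × 2s/3. The fraction is 0.033, 0.067 or 0.133.

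**4. Size for ppFEV₁, assuming s = 0.5-2 points of either sign**

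| f | s (points) | Move in average | Share of 3.0 | Share of SE 0.661 |
|---|---|---|---|---|
| 5% | 0.5 | 0.0125 | 0.4% | 0.02 |
| 10% | 1 | 0.05 | 1.7% | 0.08 |
| 20% | 2 | 0.20 | 6.7% | 0.30 |

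In the worst corner the expected estimate becomes 2.8 or 3.2, and power becomes 98.7% or 99.8%. A move of one SE at f = 20% needs s = 0.661/0.10 = 6.6 points.

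The documents give no SwCl SD or planning effect, so the SwCl move is left as a fraction of s.

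**5. Precision lost by leaving flagged values out**

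Generalized least squares over Day 15, Week 4 and Week 8, with equal variances, compound symmetry and assumed between-visit correlation ρ of 0.5-0.8. Week 8 is always kept. Late visits either fall in the same subjects at both visits or are independent.

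| Endpoint | SE increase, f = 5%, ρ = 0.8 | SE increase, f = 20%, ρ = 0.5 |
|---|---|---|
| ppFEV₁ | about 0.2% | up to 3.1% |
| SwCl | about 0.2% | up to 4.1% |

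**The case against.** The strongest reply is that item 6 is a deliberate, rarely used exception. The general pre-dose rule allows exceptions noted elsewhere, and it, 11.3 and 11.5.1 all point to 9.6.1, where item 6 sits. The 6-hour cut matches the missed-dose rule in 9.6.2, under which a later morning dose costs the evening dose. Other text also steers sites away from late visits. Spirometry is to be done at about the same time each visit, and Day 1 cannot be home-dosed, so a Day 1 slot within the 6-hour limit would tend to carry forward. A home-dosed visit cannot meet the PK window at Day 15 or Week 4, which sites must make every effort to meet. Dose times are recorded, deviations are monitored, and the SAP's list of potential important deviations is open-ended. Site manuals that are not available here may say more.

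Much of this stands. Late visits are discouraged, and those at Day 15 and Week 4 could be identified from data already collected. It does not close the gap. The spirometry and SwCl rows say must, with no carve-out, and item 6 names neither assessment. The same-time rule is approximate and covers spirometry only. The PK text makes a home-dosed visit a PK deviation but does not say what happens to its efficacy values. Even if an exception was intended, the SAP has no rule that flags, excludes or tests those values.

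A reader might go further and infer that nothing in the protocol keeps sites from booking late visits, or that the primary result is biased. The same-time and PK provisions contradict the first. For the second, the documents give neither the frequency of late visits nor the size or sign of a post-dose shift.

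**Conclusion.** The conflict is real but minor. At Day 15 and Week 4 a site that follows item 6 breaks the pre-dose rule for spirometry and SwCl, and the SAP would use the values unmarked in within-group averages. At Day -14 the consequence is negligible.

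The share of late visits, the post-dose shift and the between-visit correlations are all assumptions. Over the ranges shown, the ppFEV₁ bias stays below a third of a planning SE and power stays above 98%, so the primary conclusion is not threatened. For SwCl, only the fraction of a shift that reaches the average (3.3-13.3%) can be stated. This is an inexpensive improvement, not a defect that blocks the plan.

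**What to change.** **Protocol 9.6.1.** Add one sentence: book Day -14, Day 15 and Week 4 so that spirometry, SwCl and the clinic dose all fall within 6 hours of the usual morning dose, with that dose withheld until the assessments are done. Under 9.6.2 the evening dose is then kept. Retain home dosing only as a fallback.

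**SAP.** Use the dose times recorded with PK sampling to flag home-dosed Day 15 and Week 4 spirometry and SwCl values as post-dose. Repeat the ppFEV₁ and SwCl MMRMs without flagged values as a sensitivity analysis. No PK sample is taken at Day -14, so only the booking rule applies there.

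**Cost.** A small scheduling constraint, eased by the visit windows (±2 days at Day -14, ±3 at Day 15, ±5 at Week 4), one derived flag, and one extra model run per endpoint. No new data collection is needed.

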9.6.2 Missed Doses

If 6 hours or less have passed since the missed morning or evening dose, the subject should take the missed dose as soon as possible and continue on the original schedule.

Morning dose: If more than 6 hours have passed since the missed **morning** dose, the subject should take the missed dose as soon as possible and should not take the evening dose.

Evening dose: If more than 6 hours have passed since the missed **evening** dose, the subject should not take the missed dose. The next scheduled morning dose should be taken at the usual time.

Morning and evening doses should not be taken at the same time.

9.7 Dose Modification for Toxicity

No dose modifications for toxicity are allowed. Treatment may be interrupted as outlined in Section 9.8. If any unacceptable toxicity arises, individual subjects will discontinue dosing (Section 9.1.5).

9.8 Study Drug Interruption and Stopping Rules

In subjects who have interrupted study drug for >72 hours for any reason, the investigator should resume study drug only after a thorough investigation of the cause for interruption. The

investigator will evaluate the subject's clinical stability and should consider resumption of study drug only after the subject is clinically stable and there is no comorbidity or condition that, in the opinion of the investigator, might confound the results of the study or pose an additional risk in administering study drug to the subject.

The medical monitor should be notified of an interruption of study drug that lasts >72 hours for any reason and of the resumption of study drug after such interruption. The medical monitor should be notified of any plan to discontinue study drug.

9.8.1 Liver Function Tests

The central laboratory will notify the medical monitor of ALT or AST $>3 \times$ ULN and total bilirubin $>2 \times$ ULN that are derived from centrally submitted samples.

Subjects with new treatment-emergent ALT or AST elevations of $>3 \times$ ULN, with or without total bilirubin $>2 \times$ ULN, must be followed closely, including confirmatory testing performed by the central laboratory within 48 to 72 hours of the initial finding and subsequent close monitoring of ALT, AST, and bilirubin levels, as clinically indicated.

If a subject cannot return to the site for confirmatory testing, a local laboratory may be used. Local laboratory results must be reported immediately to the medical monitor, and the subject must have the tests repeated and sent to the central laboratory as soon as possible (ideally within 48 to 72 hours).

Study drug administration **must be interrupted** immediately (prior to confirmatory testing) if any of the following criteria are met:

- ALT or AST $>8 \times$ ULN
- ALT or AST $>5 \times$ ULN for more than 2 weeks
- ALT or AST $>3 \times$ ULN, in association with total bilirubin $>2 \times$ ULN and/or clinical jaundice

A thorough investigation of potential causes should be conducted, and the subject should be followed closely for clinical progression.

Study drug administration **must be discontinued** if the following criterion is met:

- Subsequent ALT or AST values confirm the initial elevation that satisfied the interruption rule (above), and no convincing alternative etiology (e.g., acetaminophen use, viral hepatitis, alcohol ingestion) is identified, regardless of whether transaminase levels have improved

All subjects in whom treatment is discontinued for elevated transaminases (and bilirubin, as applicable) should have these levels monitored closely until levels normalize or return to baseline.

If an alternative, reversible cause of transaminase elevation with or without increased bilirubin or clinical jaundice has been identified, study drug administration may be resumed once transaminases return to baseline or are $\leq 2 \times$ ULN, whichever is higher. Regardless of the duration of interruption, the medical monitor should be notified prior to resumption of study drug. Upon resumption of study drug, transaminases and bilirubin should be assessed weekly for 4 weeks. If a protocol-defined transaminase elevation interruption threshold recurs within 4 weeks of rechallenge with the study drug (with confirmation of the initial elevation by repeat

testing within 48 to 72 hours), then the study drug must be permanently discontinued, regardless of the presumed etiology.

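### The liver restart rule in Protocol 9.8.1 covers bilirubin and jaundice cases but sets a limit for transaminases only

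*Protocol*

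**What the plan says.** Protocol 9.8.1 lists three findings that require immediate interruption of study drug. Two concern transaminases alone: ALT or AST above 8 x ULN, or above 5 x ULN for more than 2 weeks. The third is a combination: ALT or AST above 3 x ULN "in association with total bilirubin" above 2 x ULN, clinical jaundice, or both.

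The restart rule opens with its scope: "If an alternative, reversible cause of transaminase elevation with or without increased bilirubin or clinical jaundice has been identified". It then gives its test: "study drug administration may be resumed once transaminases return to baseline" or lie at or below 2 x ULN, whichever is higher. No bilirubin value follows, and nothing says that jaundice must have cleared.

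The other controls are these:

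- **At the signal (9.8.1).** "The central laboratory will notify the medical monitor of ALT or AST" above 3 x ULN and total bilirubin above 2 x ULN. A new elevation above 3 x ULN calls for a confirmatory test within 48 to 72 hours, then close monitoring of ALT, AST and bilirubin as clinically indicated.
- **After interruption (9.8.1).** "A thorough investigation of potential causes should be conducted, and the subject should be followed closely for clinical progression". Discontinuation is mandatory if later values confirm the elevation and "no convincing alternative etiology (e.g., acetaminophen use, viral hepatitis, alcohol ingestion) is identified, regardless of whether transaminase levels have improved".
- **Before restart.** The medical monitor should be notified, however short the interruption (9.8.1). After more than 72 hours off drug, the investigator should consider restarting only a clinically stable subject who has no condition that, in the investigator's opinion, adds risk (9.8).
- **After restart (9.8.1).** "Upon resumption of study drug, transaminases and bilirubin should be assessed weekly for 4 weeks". The rechallenge rule begins "If a protocol-defined transaminase elevation interruption threshold recurs within 4 weeks of rechallenge with the study drug"; if repeat testing confirms the elevation, drug is stopped for good whatever the presumed cause.
- **At any time.** A subject with unacceptable toxicity comes off drug (9.7), and the investigator or sponsor may withdraw a subject from drug for safety (9.9).

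**The concern.** In the third trigger, bilirubin or jaundice is what turns a transaminase rise above 3 x ULN, which might otherwise only be monitored, into a mandatory stop. The restart sentence names both in its scope and omits both from its test. A stop that needs two findings can therefore be lifted, as written, on the recovery of one.

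What is at stake is the safety of individual subjects, who may be as young as 12: re-exposure to study drug before the liver finding that prompted the stop has settled. Consistency is at stake too, because in a multicenter trial sites may decide differently where no level is written. No estimand, test or planned summary depends on this.

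**Working it through.** No figure in the plan needs reproducing; the check is a comparison of rules.

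**1. Liver rules side by side**

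| Rule | ALT/AST | Total bilirubin | Jaundice |
|---|---|---|---|
| Screening exclusion (8.2, item 2) | 3 x ULN or more | 2 x ULN or more | not named |
| Third interruption trigger (9.8.1) | above 3 x ULN | above 2 x ULN (or jaundice) | present (or bilirubin) |
| Follow-up after discontinuation (9.8.1) | until normal or baseline | until normal or baseline, as applicable | not named |
| Restart (9.8.1) | baseline or 2 x ULN, whichever is higher | none | none |

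Bilirubin has a level, or a stated end of follow-up, in every row except restart. Subjects permanently off drug have it followed to recovery where applicable; for subjects about to be re-dosed, no recovery level is stated.

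**2. A test case (illustrative values)**

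A subject is interrupted at ALT 4 x ULN and total bilirubin 3 x ULN, and viral hepatitis is identified. ALT falls to 2 x ULN; bilirubin stays at 3 x ULN. Assume a baseline ALT below 2 x ULN.

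- Transaminase limit: the higher of baseline and 2 x ULN, so 2 x ULN. ALT of 2 meets it.
- Bilirubin limit: none stated, so 3 x ULN does not bar restart.
- Jaundice: none stated, so its presence does not bar restart.

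The only numerical condition is met. What remains is judgement and notification.

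**3. Does any other control set a level at restart?**

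| Control | Sets a bilirubin or jaundice limit at restart? |
|---|---|
| Identified alternative, reversible cause (9.8.1) | No. It explains the injury; it does not measure recovery |
| Bilirubin monitoring as clinically indicated (9.8.1) | No. It produces results and attaches no restart level |
| Medical monitor notified (9.8.1) | No. Notice, not approval |
| Stability and no added risk after more than 72 hours (9.8) | No. Investigator's opinion |
| Unacceptable toxicity (9.7) | No. Mandatory, but what is unacceptable is a judgement |
| Withdrawal for safety (9.9) | No. Discretionary |
| Weekly transaminases and bilirubin for 4 weeks (9.8.1) | No. Acts after re-dosing has begun |

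The SAP does not fill the gap. Its Appendix F combination of ALT or AST above 3 x ULN with total bilirubin above 2 x ULN is for summaries and governs no dosing decision.

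**4. Room for the problem to arise**

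In the Treatment Period, scheduled chemistry after the first randomized dose and before dosing ends falls at two visits, Day 15 and Week 4 (Table 3-2). The Week 8 sample comes after randomized dosing has stopped. With the target days in SAP Appendix A (15, 29 and 57) and ignoring visit windows:

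- stop at Day 15: 57 − 15 = 42 days to the Week 8 Visit;
- stop at Week 4: 57 − 29 = 28 days to the Week 8 Visit.

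Investigation, confirmation and recovery must all fit in that time. The Day 1 sample and unscheduled tests could add occasions. The documents give no rate for the combined elevation and no restart timings.

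**The case against.** The restart sentence permits; it does not instruct. It also sits under 9.8, whose assessment of stability and risk applies once an interruption passes 72 hours. Confirmatory testing alone may take 48 to 72 hours, so most interruptions of this kind would probably come under that assessment. For harm, an investigator would have to find a subject with jaundice or bilirubin above 2 x ULN stable and free of added risk, and neither the notified monitor nor the sponsor would step in. Section 9.7 also makes stopping mandatory for unacceptable toxicity, and the rash rule in 9.8.2 likewise leaves resumption to clinical judgement. No rate is shown, and the remedy is an amendment in a trial with 8 weeks of randomized treatment.

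Most of this stands, and it is why the gap is narrow. It does not close it. In this very sentence the sponsor did not leave transaminases to judgement but wrote a number, and the companion finding in the same trigger has none.

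A reader might infer two stronger points that the documents do not support.

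- **That the protocol leaves re-dosing of a jaundiced subject uncontrolled.** It does not: the controls above apply, several in mandatory terms. What is missing is a stated level.
- **That nothing could require dosing to stop for raised bilirubin after restart, so a bilirubin-alone stopping rule is needed.** Section 9.7 could require it. The absence of an interruption criterion on bilirubin alone also holds throughout the trial, not only after restart. It is a separate design choice, which the change proposed here neither criticizes nor alters.

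**Conclusion.** The point holds, narrowly. The restart rule expressly covers interruptions prompted partly by bilirubin or jaundice, limits only transaminases, and so permits re-dosing before the other part of the trigger has resolved. No other provision sets that limit.

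The size is small. Reaching the gap requires a combined elevation, an identified reversible cause, recovery of transaminases ahead of bilirubin or jaundice, time left to restart, and a judgement in favor of restarting. I take that to mean few subjects; the documents offer no rate to test it. No efficacy or safety-table result changes.

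Two assumptions carry the conclusion: that bilirubin or jaundice can outlast the transaminase rise, which the documents do not address, and that the 72-hour assessment would catch most but not necessarily all such cases, which is an inference from the confirmatory-test window. The change should be made because it is cheap and protects subjects.

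**What to change.** Add to the restart sentence in 9.8.1 that, when total bilirubin above 2 x ULN or clinical jaundice was part of the trigger, dosing may resume only once all three hold:

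1. transaminases meet the existing limit;
2. total bilirubin has returned to baseline or is below 2 x ULN, whichever is higher, or meets a stricter value set by the sponsor's medical team;
3. clinical jaundice has resolved.

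Below 2 x ULN matches the screening limit and lies under the trigger, and the higher-of wording mirrors the existing clause. It leaves little margin: a subject stopped at 2.1 x ULN could restart at 1.9. For transaminases the gap between trigger and the 2 x ULN limit is 3 − 2 = 1 x ULN. That is a reason for the medical team to consider a stricter value. In the test case, bilirubin of 3 x ULN would now hold the restart unless baseline was at least that high.

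No new assay is needed, since total and direct bilirubin are in the chemistry panel (Table 11-1). The cost is a protocol amendment under 13.2.3 (sponsor and investigator approval, submission to regulators, and IRB/IEC notification where the change significantly affects safety) and slightly later restarts, hence a few more missed doses, in a few subjects.
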